Topical antiseptics will be required as concomitant therapy during the study. Participants who were on stable doses of oral antibiotics at screening will remain on the same stable dose throughout the study.

Disclosure Statement: In this study, the 2-arm parallel treatment period is participant-blinded and investigator-blinded and is followed by a single-arm open-label extension treatment period.

Number of Participants: Approximately 100 patients will be screened to achieve approximately 63 randomized participants.

Intervention Groups and Duration:

[figure not shown]
At baseline, participants will be randomized in a 2:1 ratio to one of two treatments groups:

Approximately 42 participants will receive LY3041658 600 mg IV Q2W for 16 weeks, and Approximately 21 participants will receive placebo IV Q2W for 16 weeks.

Starting at Week 16, all participants, including those previously assigned to placebo, will receive LY3041658 600 mg IV Q2W for 20 weeks.

Data Monitoring Committee: No

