1.3. Schedule of Activities (SoA)

Table 1. Schedule of activities for the Screening Period and Treatment Period 1 of Study I7P-MC-DSAD

Visit 1 procedures may be conducted over more than 1 day as long as all activities are completed within the allowable visit tolerance.

For procedures at an early termination visit, see ETV in Table 2.

For procedures at an unscheduled visit, see V997 in Table 2. Unscheduled visits are for participants needing rescue therapy or incision and drainage.

For procedures at an unscheduled	visit, s	ee v 95	9 / IN I	abie 2.	Unsch	eduled	i visits	are 101	partic	ipants n	needing rescue therapy or incision and drainage.
Visit number	V1	V2	V3	V4	V5	V6	V7	V8	V9	V10	Comment
Weeks from randomization	-5	_	2	4	6	8	10	12	14	16	
Study day	—	1	15	29	43	57	71	85	99	113	
Visit interval tolerance (days)	≤35	_	±2	±2	±2	±2	±2	±2	±2	±2	
Fasting visit		X								X	
Informed consent	X										
Inclusion and exclusion criteria, review and confirm	X	X									
Demographics	X										
Preexisting conditions and medical history	X										
Prespecified medical history (indication and history of interest)	X										
Prior treatments for indication	X										Relevant surgical history
Concomitant medications	X	X	X	X	X	X	X	X	X	X	
Adverse events	X	X	X	X	X	X	X	X	X	X	For AESIs, additional data are collected (Section 8.3.6).
Substance use (alcohol, caffeine, tobacco)	X										
Surgical interventions related to HS		X	X	X	X	X	X	X	X	X	
Physical Evaluation											
Height	X										Without shoes.
Weight	X									X	
Vital signs	X	X	X	X	X	X	X	X	X	X	Blood pressure, body temperature, pulse rate. Vital signs should be measured after participant has been sitting for at least 5 minutes.

Table 1. Schedule of activities for the Screening Period and Treatment Period 1 of Study I7P-MC-DSAD

Visit 1 procedures may be conducted over more than 1 day as long as all activities are completed within the allowable visit tolerance.

For procedures at an early termination visit, see ETV in Table 2.

For procedures at an unscheduled visit, see V997 in Table 2. Unscheduled visits are for participants needing rescue therapy or incision and drainage.											
Visit number	V1	V2	V3	V4	V5	V6	V7	V8	V9	V10	Comment
Weeks from randomization	-5	_	2	4	6	8	10	12	14	16	
Study day	_	1	15	29	43	57	71	85	99	113	
Visit interval tolerance (days)	≤35	_	±2	±2	±2	±2	±2	±2	±2	±2	
Fasting visit		X								X	

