Table 1. Schedule of activities for the Screening Period and Treatment Period 1 of Study I7P-MC-DSAD

Visit 1 procedures may be conducted over more than 1 day as long as all activities are completed within the allowable visit tolerance.

For procedures at an early termination visit, see ETV in Table 2.

For procedures at an unscheduled visit, see V997 in Table 2. Unscheduled visits are for participants needing rescue therapy or incision and drainage.

Tor procedures at all unschedured	V1511, 5	CC V 93	7 / 111 1	able 2.	Uliscii	caurec	1 112112	are 10	partic	ipanis n	leeding rescue therapy or incision and dramage.
Visit number	V1	V2	V3	V4	V5	V6	V7	V8	V9	V10	Comment
Weeks from randomization	-5	_	2	4	6	8	10	12	14	16	
Study day	_	1	15	29	43	57	71	85	99	113	
Visit interval tolerance (days)	≤35	—	±2	±2	±2	±2	±2	±2	±2	±2	
Fasting visit		X								X	
Pharmacokinetic (PK) sample		X	X	X		X		X		X	At Visit 2, Visit 10, and Visit 19, collect samples at 3 time points:
											If a hypersensitivity event occurs, collect additional samples (see (Appendix 10.2, Section 10.2.2).
Immunogenicity (ADA) sample		X		X						X	Collect samples before dosing, if dosing is scheduled. If a hypersensitivity event occurs, collect additional samples (see Appendix 10.2, Section 10.2.2). See Section 8.9 for additional details.
Exploratory biomarker sample – Whole blood for RNA and for epigenetics,		X		X						X	
Pharmacogenetics sample (DNA)	X										
Exploratory biomarker samples - other		X	X	X		X		X		X	At Visit 2 and Visit 10, collect samples before the infusion starts.
Randomization and dosing											
Randomization		X									
Dosing		X	X	X	X	X	X	X	X	X	No dosing at Visit 1, Visit 20, ETV, or V997.

Abbreviations: ADA = anti-drug antibody; AESI = adverse event of special interest; anti-HBc = antibody to hepatitis B core antigen; ASAS = Assessment of SpondyloArthritis International Society; C-SSRS = Columbia Suicide-Severity Rating Scale; DLQI = Dermatology Life Quality Index; DNA = deoxyribonucleic acid; ECG = electrocardiogram; ETV = early termination visit; HBsAg = hepatitis B surface antigen; HIV = human immunodeficiency virus; HS = hidradenitis suppurativa; NRS = numeric rating scale; RNA = ribonucleic acid; V = visit; WOCBP = women of childbearing potential.

Table 2. Schedule of activities for Treatment Period 2 of Study I7P-MC-DSAD

For procedures at an early termination visit, see ETV in Table 2.

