6.4. Study Intervention Compliance

Participants will receive study intervention directly from the investigator or designee at the study site, under medical supervision. The date and time of each dose administered in the clinic will be recorded in the source documents and recorded in the electronic case report form (eCRF). Deviations from the prescribed dosage regimen should be recorded in the eCRF.

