### **6.9. Safety Analyses**

The general methods used to summarize safety data, including the definitions of baseline values, are described in Section 6.3.2.

Safety analyses will include data after rescue unless otherwise stated, and patients will be analyzed according to the investigational product to which they were randomized at Week 0 (Visit 2). Additional analyses may be conducted using data after rescue to systemic therapy for some safety topics such as systemic treatment-emergent adverse events (TEAEs), and serious adverse events (SAEs). Safety analyses will take place using the safety population defined in Section 6.3.1.

Safety topics that will be addressed include the following: AEs, clinical laboratory evaluations, vital signs and physical characteristics.

Unless otherwise specified, by-visit summaries will include planned on-treatment visits. For tables that summarize events (such as AEs, categorical lab abnormalities, shift to maximum value), post-last dose follow-up data will be provided for Treatment Period 1 (Week 0 to Week 16) and Treatment Period 2 (Week 16 to Week 36) separately. For deaths and malignancies, all

available follow-up data up to the end of the study will be included. Listings will include all safety data.

For selected safety assessments, descriptive statistics may be presented for the last measure observed during post-treatment follow-up (up to 30 days after the last dose of treatment including rescue, regardless of the study period).

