### **6.9.2. Adverse Events**

Adverse events are recorded in the eCRFs. Each AE will be coded to system organ class (SOC) and preferred term (PT) using the Medical Dictionary for Regulatory Activities (MedDRA) version that is current at the time of database lock. Severity of AEs is recorded as mild, moderate, or severe.

A TEAE is defined as an event that either first occurred or worsened in severity after the first dose of study treatment and on or prior to the last visit date during the analysis period. For each event classification term, the number of participants experiencing a TEAE with that classification term will be tabulated. TEAEs will be summarized by treatment period and overall for the study.

Treatment-related TEAEs are defined as events that are indicated by the investigator on the eCRF to be related to treatment. For events that are gender-specific, the denominator and computation of the percentage will include only participants from the given gender.

Adverse events are classified based upon the MedDRA PT. The MedDRA Lowest Level Term (LLT) will be used in defining which events are treatment-emergent. The maximum severity for each LLT during the baseline period up to the first dose of the study medication will be used as the baseline. If an event with missing severity is preexisting during the baseline period, and persists during the treatment period, then the baseline severity will be considered mild for determining TEAE (that is, the event is treatment-emergent if the severity is coded moderate or severe postbaseline and not treatment-emergent if the severity is coded mild postbaseline). If an event occurring postbaseline has a missing severity rating, then the event is considered treatment-emergent. The day and time for events where onset is on the day of the first dose of study treatment will both be used to distinguish between pretreatment and posttreatment in order to derive treatment-emergence. Should there be insufficient data for AE start date to make this

comparison (for example, the AE start year is the same as the treatment start year, but the AE start month and day are missing), the AE will be considered treatment-emergent.

In an overview table, the number and percentage of subjects who experienced a TEAE or serious adverse event (SAE), died due to an AE, or discontinued from the study due to an AE will be summarized by treatment.

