#### **6.9.5.5. Infusion Site Reactions**

Symptoms of a local infusion site reaction may include erythema, induration, pain, pruritus, and edema. If an infusion site event is reported, the adverse event will be recorded, and additional data will be provided to the sponsor in the eCRF. The number and percentage of patients having any ISR, and each Symptoms (erythema, induration, pain, pruritus, and edema) by maximum severity will be summarized by and treatment for Period 1 using the mITT population. Additionally, summaries of ISR and each Symptoms over by treatment will be provided for each visit.

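### The Period 1 adverse-event window closes by date at Visit 10, so same-day reactions to the first open-label LY3041658 infusion can be counted under placebo

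*SAP*

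**What the plan says.** - **Event window.** SAP 6.9.2 defines a treatment-emergent adverse event (TEAE) as one that first occurs or worsens "after the first dose of study treatment and on or prior to the last visit date during the analysis period". The same section says "TEAEs will be summarized by treatment period and overall for the study".
- **Clock time.** SAP 6.9.2 uses day and time together only for events on the day of the first dose of study treatment, to separate pretreatment from posttreatment. It has no such rule for the change of period.
- **Last visit of Period 1.** Visit 10 (Week 16, Day 113) is the last column of Protocol Table 1, titled "Schedule of activities for the Screening Period and Treatment Period 1 of Study I7P-MC-DSAD". Table 2, for Period 2, starts at Visit 11 (Week 18).
- **Dosing at Visit 10.** The dosing row of Table 1 is marked at Visit 10, and the comment beside it reads "No dosing at Visit 1, Visit 20, ETV, or V997". Visit 10 is not among the exceptions. Protocol 1.1 adds: "Starting at Week 16, all participants, including those previously assigned to placebo, will receive LY3041658 600 mg IV Q2W for 20 weeks". SAP 6.3.2 names Visit 10 as the visit of the first LY3041658 dose for former placebo participants.
- **Grouping.** SAP 6.9 analyses safety by the product randomized at Week 0. SAP 6.3.1 defines the Safety population by the intervention received within each study period.
- **Infusion-site reactions.** SAP 6.9.5.5 says these "will be summarized by and treatment for Period 1 using the mITT population", with a further summary at each visit.

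**The concern.** The drug changes for the placebo group part-way through a single calendar day, and the event window is cut by whole days. Protocol Section 8 has assessments finished before dosing, so a reaction to the Visit 10 infusion comes after the Week 16 assessments but may carry the Visit 10 date. No rule in the SAP divides that date.

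Protocol 8.3.6 lists infusion reactions and systemic hypersensitivity reactions among the adverse events of special interest. The protocol provides for acute reactions: at least 30 minutes of observation after each infusion (6.1) and sampling within 1 to 2 hours of a hypersensitivity event (10.2.2). These are events whose onset can share the infusion date. Period 2 has a single treatment group, so Period 1 is the only period with a concurrent placebo comparison, and SAP 6.9.2 compares TEAE percentages with Fisher's exact test. An active-drug reaction recorded under placebo pulls that comparison towards no difference.

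**Working it through.** The documents give no figure on this point, so there is none to reproduce. The check sets the window against the schedule and then illustrates the size.

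**1. Does the window include the open-label infusion day?**
- Day of Visit 10: 16 × 7 + 1 = 113, which matches Table 1.
- Infusion dates inside Period 1 as written: Visits 2 to 10, that is 9. Eight are blinded (Visits 2 to 9) and one is open-label active (Visit 10).
- Period 2 infusions: Visits 10 to 19, that is 10; or Visits 11 to 19, that is 9, if Visit 10 is left in Period 1.

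**2. Does either grouping rule remove the problem?**
- By randomized product (SAP 6.9), a former placebo participant is in the placebo column.
- By intervention received within the period (SAP 6.3.1), the same participant in a Period 1 table is still in the placebo column.
- The infusion-site table uses Period 1 and the as-assigned mITT population, so the result is the same.

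The two grouping rules differ and need reconciling, but the answer here does not depend on which is used.

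**3. What happens in Period 2?** The SAP does not say when the Period 2 window opens. If the first dose is read separately for each period, the event also meets the Period 2 definition and is counted twice. If Period 2 starts after the last Period 1 date, the event is missed there. Neither reading takes it out of Period 1.

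**4. Size (illustrative).**
Inputs: about 45 participants are expected to complete 16 weeks (Protocol 9.2, SAP 6.2). About 21 are randomized to placebo in the protocol and about 17 in the SAP. Equal completion across the 2:1 arms is assumed. The same-day reaction risk p is assumed to be 2% to 10%, because the documents give none.

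- Placebo completers: 45 × 1/3 = 15.
- Expected participants misassigned: 15 × p.
- Chance of at least one: 1 − (1 − p)^15.
- Points added to placebo incidence by each: 1/21 = 4.8 (protocol) or 1/17 = 5.9 (SAP).

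| Assumed p | Expected misassigned (n = 15) | Chance of at least one | Points added, of 21 | Points added, of 17 |
|---|---|---|---|---|
| 2% | 0.30 | 26% | 1.4 | 1.8 |
| 5% | 0.75 | 54% | 3.6 | 4.4 |
| 10% | 1.50 | 79% | 7.1 | 8.8 |

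If every randomized placebo participant reached Visit 10, the expected number would be 0.34 to 1.7 (n = 17) or 0.42 to 2.1 (n = 21).

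**5. Effect on a table.** Suppose 3 of 42 LY3041658 participants and 0 of 21 placebo participants react in the blinded period. The difference is 7.1 points. One misassigned event makes it 3/42 against 1/21, or 7.1 − 4.8 = 2.4 points (unrounded 7.14 − 4.76 = 2.38).

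**6. After the fix.** With Period 1 closed at the start of the Visit 10 infusion, it covers 8 infusions. The number of former placebo participants with active-drug time inside the placebo window falls from about 15 to 0.

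**The case against.** The strongest reply is that the documents already tie the Visit 10 infusion to Period 2. Period 2 is the open-label period starting at Week 16, Period 1 is described as double-blind, and the Period 2 baseline is the last value before Visit 10. A sensible programmer could place post-infusion events in Period 2. This stands as a sign of intent. None of these statements closes the Period 1 window, however, and the date rule in SAP 6.9.2 does not exclude such events.

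The week labels in SAP 6.9 ("Treatment Period 1 (Week 0 to Week 16) and Treatment Period 2 (Week 16 to Week 36) separately") put Week 16 in both periods, but the sentence concerns follow-up data after the last dose. It is weak evidence on the TEAE boundary, and the point does not rest on it.

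The likely effect on hypothesis tests is small. At 5% to 10%, about 2 to 4 of 42 LY3041658 participants would react to a first infusion. Fisher's exact test gives p = 0.55 (2/42) and 0.29 (4/42) against 0/21, and 1.0 and 0.66 against 1/21. None is significant. It takes about 8 LY3041658 reactors for one added placebo event to matter: p = 0.044 for 8/42 against 0/21, and 0.25 against 1/21.

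Other outputs would help to show such events: the infusion-site summary by visit, the hypersensitivity listing with onset dates, and the listing of all adverse events. They would expose the misassignment to a careful reader but would not correct the comparative table.

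Protocol 2.3 reports no known adverse drug reactions and one mild, short-lived infusion-associated reaction in the single-dose study, so the true rate may lie at or below the bottom of the assumed range.

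**Conclusion.** The point holds as a boundary rule that, applied as written, gives the wrong attribution for events starting after the infusion on the Visit 10 date. The illustrated effect is 0.3 to 1.5 former placebo participants. This rests on 15 placebo completers, equal completion across arms and an assumed same-day risk of 2% to 10%. Events starting the next day or later fall outside the Period 1 window.

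A reader might go further in three ways that the documents do not support:
- **That the safety contrast would reverse.** The first-infusion risk also applies to the LY3041658 arm at Visit 2, followed by seven more blinded infusions. On average the contrast narrows; it would not be expected to change sign.
- **That this undermines the trial's main purpose.** The primary objective is HiSCR response, and the secondary endpoints are AN count and skin pain. Safety is evaluated, but none of these is a safety contrast.
- **That the events are certainly lost from Period 2.** Double counting is the other reading, because the Period 2 start is undefined.

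**What to change.** In SAP 6.9.2:
- For participants who continue, end the Period 1 event window at the date and time of the Visit 10 infusion, and start Period 2 there.
- For events dated on the Visit 10 day, use onset time to assign the period.
- State one default for all event types when the onset time is missing. Assigning them to Period 2 would be in line with the existing SAP rule that an event with insufficient start-date data is taken as treatment-emergent.

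Apply the same cut to the Period 1 infusion-site-reaction table in SAP 6.9.5.5.

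The cost is a few lines of SAP text and one derivation rule. Protocol 6.4 already provides the dose times: "The date and time of each dose administered in the clinic will be recorded in the source documents", and in the eCRF as well. Onset time is already used on the first-dose day; the sponsor should confirm that it is also collected for events on the Visit 10 day. Trial conduct and the efficacy analyses do not change. The downside is small: a few events without an onset time are allocated by default, and some of these will have started before the infusion.

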4.2. Scientific Rationale for Study Design

The primary endpoint of this study is the proportion of patients achieving Hidradenitis Suppurativa Clinical Response (HiSCR) at Week 16. HiSCR is defined as at least a 50% reduction in the total abscess and inflammatory nodule count (AN count) with no increase in abscess count and no increase in draining fistulae count relative to baseline. HiSCR has been used in previous HS trials and has been accepted by the Food and Drug Administration as a primary endpoint (Kimball et al. 2014; Kimball et al. 2016a; Kimball et al. 2016b). Evaluation of the primary endpoint at the Week 16 time point is appropriate based on current clinical trials of systemic immunomodulatory therapies in HS (guselkumab NCT03628924, secukinumab NCT03713632 and NCT03713619; bimekizumab NCT04242498 and NCT04242446).

A double-blind, placebo-controlled design through the first treatment period limits bias for the participant and investigator assessments and enables a clearer interpretation of the effects of active drug.

The second treatment period (open-label) allows for evaluation of both safety and changes in efficacy over time in participants who received LY3041658 in the placebo-controlled treatment period. The second treatment period also allows participants who were randomized to placebo in the first treatment period to receive LY3041658 in the open-label period for a treatment duration similar to that of the placebo-controlled period.

The post-treatment follow-up period allows for continued safety monitoring after the last dose. The last dose is given at Week 34. This is 2 weeks before the last visit in the second treatment period (Week 36) and a total of 12 weeks before the last post-treatment follow-up visit (Week 46). LY3041658 concentrations are expected to be significantly decreased in the plasma after 5 half-lives. The terminal half-life of LY3041658 is approximately 2 weeks, based on pharmacokinetic (PK) data from the Phase 1 Study DSAB. Therefore, for the present study, the planned duration of safety follow-up is adequate, as this duration covers approximately 6 half-lives. A follow-up period of a similar duration was used after the last dose of LY3041658 in the single-dose Study DSAA and multiple-dose Study DSAB.

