8.3. Adverse Events and Serious Adverse Events

Adverse events will be reported by the participant or, when appropriate, by a caregiver, surrogate, or the participant's legally authorized representative.

The investigator and any qualified designees are responsible for detecting, documenting, and recording events that meet the definition of an adverse event or SAE and remain responsible for following up adverse events that are serious, considered related to the study intervention or study procedures, or that caused the participant to discontinue the study intervention or the study (see Section 7).

Pregnancy after maternal or paternal exposure to investigational product does not meet the definition of an adverse event. However, to fulfill regulatory requirements, any pregnancy should be reported using the SAE process described in Appendix 10.3, Section 10.3.4, to collect data on the outcome for both mother and fetus. See also Section 8.3.5.

8.3.1. Time Period and Frequency for Collecting Adverse Event and Serious Adverse Event Information

All adverse events will be collected from the time of the participant's signing of the ICF until the participant's last post-treatment follow-up visit.

Likewise, all SAEs will be collected from the signing of the ICF until the last post-treatment follow-up visit.

Adverse events that begin before the start of study intervention but after signing of the ICF will be recorded on the Adverse Event CRF.

Although all adverse events after signing the ICF are recorded by the site in the CRF/electronic data entry tool, SAE reporting to the sponsor begins after the participant has signed the ICF and has received study drug. However, if an SAE occurs after signing the ICF but prior to receiving study drug, the SAE needs to be reported ONLY if the SAE is considered reasonably possibly related to study procedures.

All SAEs will be recorded and reported to the sponsor or the sponsor's designee immediately, and under no circumstance should this exceed 24 hours, as indicated in Appendix 10.3. The investigator will submit any updated SAE data to the sponsor within 24 hours of it being available.

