Follow-up emergent adverse events, SAEs including deaths, and adverse events that lead to study discontinuation will be summarized. All adverse events, including pre-existing conditions, will be listed by participant, visit, preferred term, treatment group, severity, and relationship to the treatment.

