#### **6.9.2.1. Serious Adverse Event Analyses**

The number and percentage of patients who experienced an SAE (including the SAEs that led to death) during the study drug period will be summarized by treatment using MedDRA PT nested within SOC. Events will be ordered by decreasing frequency within SOC.

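### The SAP ends treatment emergence at the last visit date, leaves its other safety windows undefined, and specifies no table for the follow-up emergent events that the protocol says will be summarized

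*SAP*

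**What the plan says.** Several safety windows appear, and they do not match.

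- **TEAEs (SAP 6.9.2).** An event qualifies if it first occurs or worsens "after the first dose of study treatment and on or prior to the last visit date during the analysis period". The term 'analysis period' is not defined. The same section adds: "TEAEs will be summarized by treatment period and overall for the study".
- **SAEs (SAP 6.9.2.1).** Patients with an SAE "during the study drug period will be summarized by treatment using MedDRA PT nested within SOC". This 'study drug period' is not defined and is not tied to a visit. SAP 6.9.2.2 uses the same term for discontinuations of treatment due to an AE.
- **Event tables in general (SAP 6.9).** For AEs and similar tables, "post-last dose follow-up data will be provided for Treatment Period 1 (Week 0 to Week 16") and, separately, for Treatment Period 2 (Weeks 16 to 36). Only deaths and malignancies are expressly carried to the end of the study. Listings hold all safety data.
- **Protocol 9.4.5.** The treatment periods serve as the postbaseline period for the TEAE analysis. Separately: "Follow-up emergent adverse events, SAEs including deaths, and adverse events that lead to study discontinuation will be summarized".
- **Collection (Protocol 8.3.1).** "Likewise, all SAEs will be collected from the signing of the ICF until the last post-treatment follow-up visit". The same holds for AEs.

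**The concern.** A cut-off at a visit date ties the counting of an event to attendance, and attendance can itself depend on the event. Take a participant who is infused, falls ill some days later and never attends again. The site may still learn of the event and report it, but its onset is after the last visit date, so it fails the TEAE definition.

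The flag is used elsewhere. SAP 6.9.5.3 analyses treatment-emergent infections and draws potential opportunistic infections from TEAEs. Infections are an adverse event of special interest in Protocol 8.3.6, so a delayed infection would be missing from the tables meant to show it.

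The second gap is the post-treatment follow-up. Protocol 4.2 justifies that period as continued safety monitoring after the last dose, and the data are collected. Yet the SAP, which Protocol 9.4 describes as the more detailed document, defines no follow-up emergent event, no follow-up baseline and no follow-up table. Two programmers working from this text could produce different tables by arm.

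**Working it through.** **Inputs.** From the Schedule of Activities (Protocol 1.3): first dose at V2, Day 1; last dose at V19, Day 239; V20, Day 253; V802, Day 323. From Protocol 4.2: "The terminal half-life of LY3041658 is approximately 2 weeks".

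**Reproducing the plan's figures.**
- Follow-up length: 323 − 253 = 70 days = 10 weeks, as stated.
- Last dose to final visit: 323 − 239 = 84 days = 12 weeks, as stated.
- Half-lives covered: 12 / 2 = 6, as stated.

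**Completer, treatment-period reading (TEAE window closes at V20).**
- Post-dose time inside the window: 253 − 239 = 14 days, one half-life.
- Post-dose time outside: 70 / 84 = 83%.
- Scheduled post-baseline time outside: 70 / (323 − 1) = 70 / 322 = 22%.
- Assuming mono-exponential decline at the stated half-life, 0.5^1 = 50% of the post-infusion level remains at V20 and 0.5^6 = 1.6% at V802. A faster early distribution phase would make the first figure smaller.

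**Completer, study-wide reading.** If TEAEs reported overall for the study run to V802, all 84 days are inside. The text allows either reading, so the covered post-dose time is 14 or 84 days.

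**Non-returner.** Protocol Section 8 has assessments finished before dosing. If the last attended visit is a dosing visit, no event that starts after that day is a TEAE. A completer's events are counted for 14 days after the last dose even on the narrow reading.

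**Who could be affected.** Protocol 9.2 expects about 45 of 63 randomized participants to complete Period 1, so about 63 − 45 = 18 (29%) would not. That is the pool within which Period 1 non-return could arise, not the number lost. Under Protocol 7.1 those who stop drug should still have an early termination visit (ETV) and the follow-up visits. Under Protocol 7.2 the ETV at study withdrawal is done if possible. No rate of complete non-return is given.

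**Early leaver who does attend.** Suppose, for illustration, that the ETV falls at Week 10. V801 is then at Week 14 (10 + 4) and V802 at Week 20 (10 + 10). The SAP does not say whether the Period 1 analysis period ends at the ETV, at Week 16 or at V802.

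**Whether another SAP rule closes the gap.** The 30-day post-dose window in SAP 6.9 would reach Day 269, 16 days past V20. It covers only optional descriptive statistics on the last measure for selected assessments. SAP 6.14 summarizes SAEs by treatment group whether or not they are TEAEs, but its non-serious events must be TEAEs.

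**The case against.** A reader might infer that the SAE tables also close at the last attended visit, that everything in the 10-week follow-up except deaths and malignancies disappears, and that event rates are therefore biased low or biased between arms. The documents do not support this.

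- The last-visit rule defines a TEAE. The SAE table has its own window, and the overview table in SAP 6.9.2 gives no visit cut-off for its SAE count. The registry summary counts SAEs regardless of TEAE status. Loss of non-returners' SAEs from the SAE table is a possible reading of an undefined term, not what the text states.
- SAP 6.9 says event tables will include data after the last dose. Its week ranges can be read as naming the periods rather than truncating the data. TEAEs are also reported over the whole study, and listings retain every AE and SAE.
- Protocol 9.4.5 itself makes the treatment periods the postbaseline period for TEAEs. A treatment-period TEAE window is therefore consistent with the protocol, and follow-up emergent events form a separate category.
- For completers, Weeks 36 to 46 follow open-label drug in both randomized arms, so leaving them out does not distort the placebo-controlled comparison. An on-treatment rate has a different definition; it is not a biased estimate of a longer-window rate.

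All of this stands and limits the point. It does not answer three things: treatment emergence depends on a visit date, two governing terms are undefined, and the protocol's follow-up emergent summary has no counterpart in the SAP. Listings preserve the events but give no rates by arm.

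**Conclusion.** The point holds in a limited form. Applied literally, the TEAE rule excludes events that start after a non-returner's final visit, and that exclusion carries into the infection and opportunistic-infection tables. SAEs in such participants may also be missing from the SAE table, depending on what the study drug period is taken to mean. The SAP does not specify the follow-up emergent summary in Protocol 9.4.5.

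The 83% and 22% figures are shares of scheduled time for a completer. They rest on the treatment-period reading of the undefined analysis period. They are not shares of events: the documents give no event counts, so neither the number of events affected nor any between-arm bias can be computed. The matter is still more than a wording preference, because the choice of window decides which events are tabulated by arm. It should be settled in the SAP.

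**What to change.** 1. In SAP 6.9.2, 6.9.2.1 and 6.9.2.2, define the analysis period and the study drug period by dates anchored to dosing. One workable choice runs from first dose to last dose + 14 days, with Period 1 closed at the first open-label dose if there is one. For a completer this ends on Day 253, the scheduled V20, so it keeps the treatment-period window that Protocol 9.4.5 supports.
2. State that events in the window count whether or not a later visit was attended.
3. Add a follow-up emergent table of AEs, SAEs and AEs leading to study discontinuation, from the end of that window to V802 or last contact. Present it by randomized arm and by the period of the last dose, and define the baseline against which worsening is judged.
4. Consider showing adverse events of special interest in that table. This is a sensible addition, but Protocol 9.4.5 does not promise it.

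The cost is SAP wording and one extra table set from data already collected. Reported event counts may be slightly higher.
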